### 7.1 Arm 1 Treatment: 7+3

#### 7.1.1 Remission Induction

- Daunorubicin 60 mg  $\text{m}^2/\text{day}$  IV Days 1-3 (total dose 180 mg/ $\text{m}^2$ )
- Cytarabine 100 mg/ $\text{m}^2/\text{day}$  CIVI Days 1-7 (168 hour infusion, total dose 700 mg/ $\text{m}^2$ )

During the Remission Induction, a bone marrow examination (aspirate and biopsy) on Day 14 (+3 days) is required in all patients. Recommendations regarding the need for second induction are provided in the table below. Consult with the study chair if there are questions about the need for reinduction,

Bone Marrow Cellularity	Bone Marrow Leukemic Blasts	Action
$\geq 20\%$	$\geq 5\%$	Second remission induction
	$< 5\%$	Do not start second remission induction therapy. Repeat bone marrow biopsy upon count recovery or by Day 42
$< 20\%$	$\geq 5\%$	Repeat bone marrow biopsy in one week, and follow guidelines in table.

	< 5%	Do not start second remission induction therapy. Repeat bone marrow biopsy upon count recovery or by Day 42
--	------	---

Patients with residual disease as indicated above on Day 14 or subsequent biopsy following the first course of induction chemotherapy are eligible to receive a second remission induction course. It is recommended that a second induction course start within 7 days of bone marrow documentation of residual disease but may be delayed based on the clinical status of the patient. Removal of a patient following a single cycle of induction chemotherapy to receive non-protocol therapy is highly discouraged as the results of the day 14 bone marrow (i.e. high cellularity, blast percentage) do not predict the outcome of second remission induction course.

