### 13.1.1 Primary Endpoint

- Phase II component: Event-free survival (EFS). EFS is defined as the time from the date of randomization to the first of failure to achieve a CR/CRi during induction, relapse, or death due to any cause, with patients last known to be alive and event-free censored at the date of last contact. Patients who are removed from protocol treatment for allogeneic HCT or azacitidine per [Section 8.1.1](#) will not be censored for EFS, and will be continued to be followed for relapse or death. Patients who receive other non-protocol therapy without relapse or CR/CRi during induction will be censored at the time they discontinue the treatment. All randomized patients meeting the eligibility criteria will be evaluable for the primary endpoint (EFS) analysis based on an intention to treat.
- Phase III component: Overall survival (OS) – measured from the date of randomization to death from any cause, with patients last known to be alive censored at the date of last contact. All randomized patients will be evaluable for this endpoint.

*As of Amendment 04, there will be no additional accrual to the Phase III component of the trial regardless of the outcome of the Phase II analysis.*

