## 13.2 Analysis Plan

### 13.2.1 Primary Endpoint

The analysis for both phase II and III component would be intention-to-treat (ITT), which means that all patients who signed a consent form and are randomized are included in the analysis and will be analyzed in the arms to which they are randomized.

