### 13.2.2 Secondary Endpoints

- 1-year EFS rate:** The 1-year EFS rate is the proportion of efficacy evaluable patients event-free 1 year from registration. Patients who fail to achieve a CR/CRI during the induction, relapse, or die prior to 1 year after randomization/registration will be considered as a failure for this endpoint. Patients who are removed from protocol treatment for allogeneic HCT will continue to be followed for relapse or death at 1 year. Patients who are removed from study for other non-protocol therapy without relapse or CR/CRI during induction are also considered as a failure for the 1-year EFS endpoint.
- Disease-free survival (DFS):** DFS will be calculated as the time from achieving a CR/CRI to the time of relapse and/or death. Any patients who have not achieved the event of interest will be censored at the time of their last evaluation.
- Complete Remission (CR) and overall response rates:** Response to treatment will be assessed according to the Revised Recommendations of the International Working Group for Diagnosis, Standardization of Response Criteria, Treatment Outcomes, and Reporting Standards for Therapeutic Trials in Acute Myeloid Leukemia.
- Toxicity and tolerability:** As per NCI CTCAE v5.0, the term toxicity is defined as adverse events that are classified as either possibly, probably, or definitely related to the study treatment. The maximum grade for each type of toxicity will be recorded for each patient, and frequency tables will be reviewed to determine toxicity patterns. In addition, we will review all adverse event data that is graded as 3, 4, or 5 and classified as either “unrelated” or “unlikely to be related” to study treatment in the event of an

actual relationship developing. The incidence of severe (grade 3+) adverse events or toxicities will be described for each treatment arm, but will also be compared between the arms. Fisher's exact tests will be used to quantitatively compare the incidence of severe as well as specific toxicities of interest between the treatment arms and we will graphically assess differences in maximum grades observed for toxicities between the arms. Toxicity and tolerability will be monitored regularly. The study will be reviewable by the Alliance DSMB every 6 months to identify any toxicity or tolerability issues in either of the treatment arms.

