### 13.2.4 Sensitivity Analysis

To evaluate the impact of off-protocol transplantation, sensitivity analyses will be conducted. Approaches will include but not limited to: 1) considering transplantation as a competing risk, 2) censoring patients who go off study for transplant without relapse at the time they discontinue the treatment, 3) multi-state model. In addition, the proportion of patients who received transplantation in the two arms will be summarized and compared using a chi-square test. We acknowledge that censoring patients at the time of HCT may potentially lead to informative censoring and biased efficacy results. Similar sensitivity analyses will be conducted for patients who take other off-protocol treatment due to MRD.

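### Section 13.1.1 can be read to censor induction failures who switch therapy, although the same bullet counts induction failure as an EFS event; no precedence rule or failure date settles it.

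*Combined protocol and SAP*

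**What the plan says.** Section 13.1.1 defines EFS as time from randomization to "the first of failure to achieve a CR/CRi during induction, relapse, or death due to any cause". Patients alive and event-free are censored at last contact. Removal for allogeneic transplant, or for oral azacitidine under section 8.1.1, does not censor. For other therapy the bullet adds: "Patients who receive other non-protocol therapy without relapse or CR/CRi during induction will be censored at the time they discontinue the treatment".

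The other relevant places are:

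- **Section 13.2.2 (1-year EFS rate):** "Patients who are removed from study for other non-protocol therapy without relapse or CR/CRI during induction are also considered as a failure".
- **Sections 7.1.1 and 7.2.1:** the marrow instruction is "Repeat bone marrow biopsy upon count recovery or by Day 42". This is management text and is not tied to EFS. On leaving early: "Removal of a patient following a single cycle of induction chemotherapy to receive non-protocol therapy is highly discouraged".
- **Section 11.4:** treatment failure is classified by cause, with no EFS date.
- **Section 13.2.4:** sensitivity analyses are planned for transplant, then "Similar sensitivity analyses will be conducted for patients who take other off-protocol treatment due to MRD".

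**The concern.** A patient who leaves induction without CR/CRi for other therapy fits both the event definition and, on its literal wording, the censoring sentence. Two analysts following the text could therefore report different primary EFS results from the same data.

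Who leaves a failing induction is unlikely to be random, and in an open-label trial it may depend on the arm. If it does, censoring removes poor-prognosis patients unequally and can move the log-rank test and hazard ratio in either direction. None of the sensitivity analyses named in section 13.2.4 would expose this. EFS still decides whether the regimen is called promising (one-sided p < 0.10, section 13.2.1). It is also the key secondary endpoint tested if OS is significant (section 13.2.3).

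**Working it through.** **1. The plan's own figure.** Section 13.1.2 states 96% power for HR 0.64 at one-sided 10%; section 13.2.1 sets 191 events.

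- Freedman: z = √191 × (1 − 0.64)/(1 + 0.64) − 1.282 = 3.034 − 1.282 = 1.752, power 96.0%.
- Schoenfeld: z = (√191/2) × |ln 0.64| − 1.282 = 3.084 − 1.282 = 1.802, power 96.4%.

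The figure reproduces. Nothing below depends on it being wrong.

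**2. Can precedence be derived from the text?** Taking the first of several events settles precedence only if each has a date. Relapse and death do; induction failure does not. Section 11.4 gives causes and sections 7.1.1/7.2.1 give marrow timing, but neither sets an EFS date. On the literal reading, a failure documented before the switch is an event, and the same failure not yet documented is censored.

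**3. How many patients could be affected?** Inputs:

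- 131 per arm and control 1-year EFS 30% (section 13.1.2).
- CR/CRi 55%, an assumption: the midpoint of the 50–60% in section 1.1. Sections 14.3.4 and 14.3.3 assume 60% and 70%, which leave fewer non-responders.
- Induction mortality 10% to 17.5%, an assumption. Section 1.3 reports 8% and 12% at 30 and 60 days in 25 earlier patients and cites 15–20% as commonly reported. Patients who die in induction cannot switch.
- Share of surviving non-responders who switch: an assumption; the documents give none.

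Non-responders per arm: 131 × 0.45 = 59. Deaths: 131 × 0.10 = 13 or 131 × 0.175 = 23. Survivors: 46 or 36. Switching of 20% control v 40% experimental is then about 9 v 18 patients, or 7 v 14.

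**4. Error rate under literal censoring, no true effect.** Simulation, 4,000 trials per scenario:

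- Non-responders have their event at 1.2–1.6 months; switchers leave at 0.5–1.2 months.
- Responders fail exponentially from 1.4 months, with 0.55 × exp(−10.6λ) = 0.30, so λ = ln(0.55/0.30)/10.6 = 0.057 per month.
- Follow-up is 24–54 months; the test is a one-sided 10% log-rank.
- Standard error is √(p(1 − p)/4000), about 0.5–0.6 percentage points, so read the figures to about one point.

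| Switching, control v experimental | Induction mortality | None documented first | Half | Three quarters |
|---|---|---|---|---|
| 20% v 40% | 10% | 21% | 15% | 12% |
| 20% v 40% | 17.5% | 18% | 15% | 11% |
| 10% v 15% | 10–17.5% | 10–12% across columns | | |
| 40% v 20% | 10–17.5% | 4–9% across columns | | |
| Equal | 10–17.5% | near 10% across columns | | |

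**5. Choice of event date.** These runs applied the shares to all 59 non-responders, so they overstate size but show direction. Dating the failure at the switch gave 6–8% error for 20% v 40% and 12–14% for 40% v 20%, so the switch date is not neutral. One common date gave 10–11% throughout. That date was 1.4 months (about 43 days), and no second induction course was modelled.

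**The case against.** **The sentence may not cover induction failures at all.** Section 13.1.1 reserves its general censoring for event-free patients and takes the first event. Section 13.2.2 lists patients who fail to reach CR/CRi and then adds the other-therapy group as a further category, which suggests patients with no event yet. Section 13.2.4 expects off-protocol therapy for MRD, which fits responders. This stands as a plausible reading, so the documents do not support saying that the plan definitely censors induction failures. But the sentence does not limit itself in that way, and without a failure date the reader cannot supply the limit.

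**Sections 13.1.1 and 13.2.2 need not conflict.** A binary rate can score as failures patients whom a time-to-event analysis censors. That is right, so section 13.2.2 is supporting evidence and not proof of contradiction.

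**Many failures will be documented first.** Section 12.1 makes resistant disease a reason to stop, and marrow examination is required. Leaving after one course is discouraged. The no-failure-documented column is therefore an extreme case, and the error falls to about 15% or less once half are documented.

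**A reader might infer a 26% false-positive rate.** That figure comes from applying 20% v 40% to all 59 non-responders per arm, including those who died in induction. Restricting to survivors gives 18–21%.

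**A reader might also infer lost power.** The final analysis is set by event count, so censoring would first delay the trigger. With equal 20% switching, simulated power for the design alternative (1-year EFS 30% v 47%) stayed at 96–99%.

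**Conclusion.** The point holds as an unresolved overlap in a primary endpoint definition, with no date for induction failure to resolve it. Confidence in that is high.

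Confidence in the size is much lower, because every switch rate is assumed. The error is materially raised only if switching is clearly more frequent in the experimental arm and failures are often undocumented at the switch. Under modest imbalance the effect is small, and the opposite imbalance makes the test conservative.

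OS carries no such rule. Accrual closed under Amendment 04 whatever EFS shows, and confirmatory EFS testing requires a significant OS result. The point should be fixed, but it does not invalidate the design.

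**What to change.** Before data lock (target August 12, 2024) or, if lock has passed, disclosed with both versions reported:

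1. State in section 13.1.1 that patients who leave induction, including any second course, without CR/CRi for other anti-leukaemia therapy have an EFS event, and that this takes precedence over censoring.
2. Date all induction failures, switchers or not, by one pre-specified, arm-neutral rule that allows for a second induction course and does not use the switch date. A common fixed time from randomization is one option.
3. Keep a separate, explicit rule for patients in CR/CRi who start other non-protocol therapy, so that the edit does not remove it.
4. Run the censoring version as a labelled sensitivity analysis and report the number affected by arm.

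The change should be documented and made without access to arm-level EFS.

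**Cost.** A few sentences; section 12.2 already requires reasons and dates of discontinuation on the CRF. A primary endpoint rule is clarified late in an open-label trial, and absolute EFS will read slightly lower. No power is gained: in the simulations on all non-responders, an effect on remission alone (55% to 65%) with equal 20% switching gave 36% with a common date against 37–40% with censoring. The gain is one reproducible result and a steadier error rate.

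**Separately,** reconcile the EFS analysis set. Section 13.1.1 says "All randomized patients meeting the eligibility criteria will be evaluable for the primary endpoint (EFS) analysis based on an intention to treat", while section 13.2.1 says "all patients who signed a consent form and are randomized are included in the analysis".

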### 13.1.2 Sample Size and Power Justification

#### Phase II component

Patients will be randomized to receive daunorubicin and cytarabine or the novel regimen with equal allocation using a permuted block method. E2906 study reported a 1-year EFS of 29%. Therefore, we estimate that the 1-year EFS in the daunorubicin and cytarabine arm will be 30%. We are interested in testing the alternative hypothesis that the 1-year EFS in the novel experimental arm will be at least 47% (a 17% improvement in the 1-year EFS). This translates to an improvement in the median EFS from 7 to 11 months (HR = 0.64), assuming exponential distributions of EFS in both control and experimental arm. A sample size of 131 evaluable patients per arm (262 total) provides 96% power to detect an improvement in median EFS from 7 months to 11 months (a hazard ratio of 0.64), using a one-sided log-rank test at a significance level of 10%.

#### Phase III component

A median OS of 12 months is anticipated on the control arm. We are interested in testing the alternative hypothesis that the median OS in the novel experimental arm will be at least 16 months (a 33% improvement in the median OS, for a HR of 0.75). This translates into an improvement in the 1-year OS from 50% to 60%, assuming exponential survival. A randomized trial comparing the novel agents passing the Phase II component against the standard arm (daunorubicin and cytarabine) will be conducted using a 1:1 randomization

scheme. A sample size of 335 evaluable patients per arm (670 total) provides 90% power to detect an improvement in median OS from 12 months to 16 months (a hazard ratio of 0.75), using a one-sided log-rank test at a significance level of 2.5%. The overall power for the phase II/III design is 86% ( $=0.96*0.9$ ). The total sample size for the Phase III component will include the patients rolled over from the Phase II component.

*As of Amendment 04, there will be no additional accrual to the Phase III component of the trial regardless of the outcome of the Phase II analysis.*

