#### Phase II component

**Final analysis:** The Phase II decision-making will be conducted when at least 191 events are observed (approximately expected 37 months after the first patient enrolled). If less than 191 events are observed 2 years after Phase II accrual ends, then the Phase II decision will occur at the target data lock.

At the final analysis of the Phase II, it will be concluded that the experimental arm regimen is promising, if we a one-sided p-value  $< 0.10$  from the log-rank test favoring the experimental arm.

*As of Amendment 04, there will be no additional accrual to the Phase III component of the trial regardless of the outcome of the Phase II analysis. Given the maturity of follow-up on the current patients and no additional accrual to the trial, the final Phase III OS analysis will also be performed at the time of final Phase II EFS analysis. All Phase III alpha (one-sided 2.5%) will be spent at this analysis. The target data lock date is August 12, 2024.*

**Interim analysis:** We will conduct a futility interim analysis which will take place after 50% of the total events have occurred (approximately 25 months after the first patient enrolled). If at the planned interim analysis the hazard ratio is  $>1.0$  in favor of the control arm, the recommendation will be to stop further accrual to the experimental arm and conclude that the novel regimen does not have improved EFS.

We will suspend accrual between phase II and III. In order to protect the phase III comparison, the results of the phase II portion will only be released to the FDA and/or industry sponsors for regulatory purposes, contingent upon the approval and recommendation from the Alliance Data Monitoring Committee. Other than that, the Alliance DMC will only release whether the criteria for continuation to Phase III have been satisfied and not any of the actual results.

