#### Phase III component

The final analysis will be conducted after 521 deaths have been observed. In addition, we will conduct 2 interim analyses which will take place after approximately 50% and 75% of the total events have occurred. The first interim analysis is for futility only, and the second interim for both futility and efficacy. If in the second interim evaluation, sufficient evidence (per criteria outlined below) is observed that the experimental arm is superior to the control arm in terms of OS, then accrual to the control arm may be suspended and terminated. To preserve the Type I error rate control on superiority, the Lan-DeMets error spending function with the O'Brien-Fleming stopping boundaries is utilized. Futility boundaries

have also been developed for the comparison against control, where if at any of the planned interim analyses the hazard ratio is  $>1$  in favor of the control arm, the recommendation will be to stop further accrual to the experimental arm (if the trial is still accruing) and conclude that the novel regimen does not have improved OS. At the final analysis, if we observe a p-value  $\leq 0.022$  from the log-rank test (equivalently,  $HR \leq 0.838$  favoring the experimental regimen, assuming the exponential distribution) we will conclude that the novel regimen significantly improves the OS, compared to the daunorubicin and cytarabine arm. The interim and final analysis boundaries and characteristics were generated using the East clinical trial software program (version 6.3, Cytel Inc).

Information Fraction	Cum. events	Cum. alpha spent	Cum. beta spent	Efficacy Boundaries			Futility Boundaries	
				HR	P-value	Z score	HR	p-value
50%	261	0	0.01	NA	NA	NA	1	0.5
75%	391	0.010	0.011	0.789	0.010	-2.339	1	0.5
100%	521	0.025	0.1	0.838	0.022	-2.012	0.838	0.022

As of Amendment 04, there will be no additional accrual to the Phase III component of the trial regardless of the outcome of the Phase II analysis. Given the maturity of follow-up on the current patients and no additional accrual to the trial, the final Phase III OS analysis will also be performed at the time of final Phase II EFS analysis. The final Phase III of analysis of OS will conclude that the novel regimen significantly improves the OS compared to the daunorubicin and cytarabine arm if the one-sided p-value from the stratified log-rank test is  $< 0.025$ . The target data lock date is August 12, 2024.

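### After Amendment 04 the OS test rests on the Phase II patients alone, yet the plan still states 90% OS power and leaves the 521-death rule unmarked

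*Combined protocol and SAP*

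**What the plan says.** **Power (13.1.2).** For Phase III the section states: "A sample size of 335 evaluable patients per arm (670 total) provides 90% power to detect an improvement in median OS" from 12 to 16 months (HR 0.75, one-sided 2.5%). It then says "The overall power for the phase II/III design is 86" percent, as the product 0.96 × 0.9. For Phase II the basis is "A sample size of 131 evaluable patients per arm (262 total"). Amendment 04 adds one line to 13.1.2, that Phase III accrual will not continue whatever Phase II shows. It gives no new sample size, death count, power or detectable HR.

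**Population (13.1.1).** For OS, "All randomized patients will be evaluable for this endpoint". The cover page of the update closes the study permanently to accrual, so the OS population is whoever has already been randomized.

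**Analysis rule (13.2.1).** The Phase III part still opens with the original rule: "The final analysis will be conducted after 521 deaths have been observed". Interim looks at 261 and 391 deaths, a boundary table and a final cut-off of p ≤ 0.022 (HR ≤ 0.838) follow. The Amendment 04 paragraph comes after these. It says "the final Phase III OS analysis will also be performed at the time of final Phase II EFS analysis" and sets a stratified log-rank test at one-sided p < 0.025. The Phase II part adds "All Phase III alpha (one-sided 2.5%) will be spent at this analysis" and "The target data lock date is August 12, 2024". Nothing marks the earlier text as superseded.

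**The concern.** The 90% and 86% are the only OS power figures in the plan, and the design they describe no longer exists. The 86% has also lost its logic. It multiplies the two powers because Phase III used to depend on passing Phase II, whereas the OS test is now run whatever the Phase II result.

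The trial is labelled an FDA registration study, and OS is its confirmatory endpoint. Under 13.2.3, OS also gates the formal EFS test at 0.025, so OS power limits the chance of both confirmatory claims. A non-significant OS result read against a stated 90% would look like much stronger evidence of no benefit than the data can supply.

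The leftover cut-off adds a second risk. An HR of 0.838 meant significance at 521 deaths, but it does not at the number of deaths now possible.

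**Working it through.** **Inputs.** HR 0.75, medians 12 and 16 months, one-sided 2.5%, 670 patients (13.1.2, Phase III). 262 patients (13.1.2, Phase II). 521 deaths and the boundaries (13.2.1). Accrual of 5, 10, then 14 per month (13.3). 54 patients accrued by 22 November 2019 (14.3.4). Data lock 12 August 2024 (13.2.1). 1:1 allocation (13.1).

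**Formulas (Schoenfeld, 1:1, d deaths).**
- Power = Φ(½√d × |ln 0.75| − 1.96), with |ln 0.75| = 0.2877
- Largest significant HR = exp(−2 × 1.96/√d)
- Deaths needed = 4(1.96 + z)²/0.2877²

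**Step 1: the original figures reproduce.**
- At 521 deaths: Φ(3.283 − 1.96) = 0.907 before interim looks. Simulating the three-look design gives 0.901 with binding futility and 0.903 without.
- exp(−2 × 2.012/√521) = 0.838, the plan's boundary.
- 0.96 × 0.9 = 0.864.

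**Step 2: deaths needed.** For HR 0.75, 90% power needs about 508 deaths and 80% about 380. In 262 patients neither 521 nor 391 deaths can occur, and the 261-death look would need almost every patient to have died.

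**Step 3: deaths expected.** Accrual is 12 × 5 + 12 × 10 = 180 by month 24. Then 82/14 = 5.9 more months reach 262 at month 29.9, and 120/14 = 8.6 reach 300 at month 32.6. Deaths are summed over entry times under exponential survival, half the patients at each median, with no loss to follow-up.

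Two ways of placing the lock:
- 24 to 36 months after accrual ends. The lower end follows the clause in 13.2.1 that sends the decision to the target lock if 191 EFS events have not occurred 2 years after accrual ends.
- By date. 54 patients at 5 per month is month 10.8; 22 November 2019 to 12 August 2024 is 56.7 months; the sum is month 67.5.

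**Step 4: power for HR 0.75.**

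| Patients | Lock | Deaths | Power | Largest significant HR |
|---|---|---|---|---|
| 262 | accrual end + 24 months | 214.2 | 55.8% | 0.765 |
| 262 | accrual end + 36 months | 235.3 | 59.7% | 0.775 |
| 262 | month 67.5 | 237.3 | 60.1% | 0.775 |
| 262 | all have died | 262 | 64.4% | 0.785 |
| 300 (assumed) | accrual end + 24 months | 247.4 | 61.9% | 0.779 |
| 300 (assumed) | accrual end + 36 months | 270.6 | 65.8% | 0.788 |
| 300 (assumed) | month 67.5 | 269.0 | 65.5% | 0.787 |
| either | slower deaths (assumed) | 191 | 51.1% | 0.753 |

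Worked line: d = 235.3 gives ½√235.3 = 7.670; 7.670 × 0.2877 = 2.206; Φ(2.206 − 1.96) = 0.597.

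An unstratified log-rank simulation (4,000 runs) gives 0.539 and 0.588 for 262 patients and 0.617 and 0.653 for 300, at +24 and +36 months. These lie within 2 points of the formula.

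**Step 5: the leftover cut-off.** At 237 deaths an observed HR of 0.838 gives z = ½√237 × |ln 0.838| = 1.36, one-sided p about 0.087. An observed HR between about 0.775 and 0.838 would meet the printed HR limit and fail the governing test.

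**Minor: E-selectin (14.3.3).** The 88% rests on 536 samples, 80% of 670. With effect size 0.3, 70% remission and two-sided 0.05, the normal approximation gives 89% at 536, 51% at 210 (80% of 262) and 41% at 160 (80% of the 200 substudy patients in 14.3.4).

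**The case against.** The best defence is that nothing here was calculated wrongly. The 90% is tied in its own sentence to 670 patients, and the same section then says that accrual has ended, so a reader is warned that the premise will not be met. The governing OS rule is explicit and dated, and spending all the alpha at one analysis leaves none for the 391-death look. Test, alpha and type I error are intact, no sample-size decision remains, and the reported HR with its confidence interval will show the precision. The actual number randomized and the deaths so far are not in the documents, so any replacement figure rests on assumptions.

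Much of this stands. The original figures are correct for the original design, and a careful reader can tell which rule governs. The low end of the range may also be pessimistic. Section 14.3.4 assumes 18 more months of accrual after November 2019, which puts the lock about 39 months after accrual ends, with about 239 deaths and 60% power at 262 patients.

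It does not remove the point. The reader can infer that power has fallen, but not by how much, and the critical HR is not stated anywhere. The uncertainty about numbers does not rescue the 90% either: 300 patients, all dead, would give only 70%. Nor is restating power foreign to this plan, since 14.3.4 already does so for MRD on the Phase II sample (63% and 65%).

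**Conclusion.** The concern holds. The stated 90% and 86% belong to a design that Amendment 04 ended, and no figure replaces them. With the planned 262 patients, OS power for HR 0.75 is about 56 to 60%, which is 30 to 34 points below 90% and 26 to 30 below 86%. It cannot exceed 64%. With an assumed 300 patients it is 62 to 66%, which is 24 to 28 points below 90% and 20 to 24 below 86%. The largest HR that reaches significance is about 0.77 to 0.79, not 0.838.

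These figures assume the planned accrual rates, exponential OS with medians 12 and 16 months and no loss to follow-up. If deaths run slower, power is lower (51% at 191 deaths).

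The fault lies in a stated property of the design and in leftover decision text. Validity of the test is not in question. It should be corrected because this is the confirmatory endpoint of a registration study. The E-selectin figure is a minor matter of the same kind.

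**What to change.** **In 13.1.2**, add a statement along these lines:

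> As of Amendment 04 the 90% and 86% figures no longer apply. With [number] patients randomized and about [D] deaths expected at the data lock, the stratified log-rank test at one-sided 2.5% has about [x]% power for HR 0.75, and significance requires an observed HR of about [y] or lower.

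The sponsor fills the brackets from the actual number randomized and the death count pooled over arms, without a look at the treatment comparison. The figures given here are only a planning guide. The statement carries most weight if written before the data lock.

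**In 13.2.1**, label the 521-death trigger, the two OS interim looks, the boundary table and the p ≤ 0.022/HR ≤ 0.838 rule as original design, superseded by Amendment 04. The stratified log-rank test at one-sided p < 0.025 is then the sole OS rule.

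**Optional, in 14.3.3**: restate the exploratory E-selectin power for the Phase II substudy sample.

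**Cost.** Wording and a less favourable stated power. No new patients, data, test or threshold, and the original design stays visible.
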